5.3.5. Sensitivity Analysis

We will refit Models 1 and 2 to evaluate the odds of the event of interest at 90 days post angioplasty among those allocated to IV isotonic sodium bicarbonate therapy compared to those allocated to IV isotonic saline, and among those allocated to NAC compared to those allocated to Placebo. The primary analysis will be repeated under 5 different scenarios as follows and the results will be displayed in a Forest plot.

(1) On the first “per-Protocol” sample with 80-120% adherence as defined in **3.4** to evaluate efficacy among those adherent to the protocol. Subjects who are over-adherent ($\geq 120\%$) or have had a non-protocol administration of study medication, particularly IV sodium bicarbonate, will be excluded.

(2) On the second “per-Protocol” sample with $\geq 80\%$ adherence as defined in **3.4** including those subjects who are over-adherent or have had a non-protocol administration of study medication, particularly IV sodium bicarbonate.

(3) On the “ITT” cohort that includes those with the initial 90-day blood sample but are missing the confirmatory sample.

(4) On the “ITT” cohort assuming all those with missing endpoint data had events before 90 days (the worst case scenario), and

(5) On the “ITT” cohort assuming all those with missing endpoint data had no events before 90 days (the best case scenario)

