#### Adjustment for Lost to Follow-Up

Because follow-up does not require a return to the VA medical center after the index angiogram and can be accomplished through electronic medical record review, telephone contact of patients, and mobile blood draws, we expect losses to follow-up to be uncommon and have estimated them to be 3%. Accounting for this estimated loss to follow up rate, our adjusted sample size will be 7,680. The study will permit secondary analysis of any SCr values assayed at a local laboratory that fit specimen collection timeframes for those blood specimens that were unable to be collected for analysis by the central laboratory.

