#### Analytic reports

Analytic reports will provide the proportions, the differences among proportions, the odds ratios, and the 95% confidence intervals for each of the summary statistics. This will be followed by a report of the results of confirmatory analyses. The confirmatory exploratory analyses will add to the basic model, factors related to disease severity, demographic and anthropomorphic measures, and structural factors such as medical site. The regression modeling we shall employ will include a model with treatment by covariate terms to explore the possibility of treatment by covariate effects (that is, exploration of potential subgroup effects). We will test that results vary or do not vary significantly by medical site. Finally we will explore the effect of including site as a random effect by extending logistic regression to generalized linear models that treat site as a random effect.

[figure not shown]
Losses to follow up and missing data

We conservatively estimate that up to 3% of subjects may be lost to follow up before 90 days. The site coordinators will make every effort to locate such subjects including at least three telephone contact attempts and one registered letter. Research staff are permitted to mail a letter to the participant for the purpose of appointment scheduling/reminders or follow-up contact. If such efforts fail and we have no information indicating the outcome for these subjects, then we will exclude them from the primary analysis and then carry out a worst case analysis to confirm the result of the primary analysis.

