5.1. Handling of Missing Data in Analysis

Up to 3% of subjects have been estimated to drop out prior to end of follow-up before 90 days. Distribution of subjects lost to follow-up and missing data on key variables across the treatment groups will be monitored throughout the study.

Missing endpoint data will not be imputed. All those with missing endpoint data either due to attrition or active withdrawal of consent will be excluded from primary analysis. Those who completed 90 days of follow-up and have initial 90 day blood-draw demonstrating a $\geq 50\%$ increase in serum creatinine but are missing the confirmatory blood draw will not be included in the primary analysis as having met the primary endpoint, however, they will be included in the sensitivity analysis as having met this endpoint data. See section 5.3.5.

5.2. Univariate and Bivariate Distributions of Baseline, Procedure Related, Safety and Follow-up data

- In general, the number of observations, mean, median, standard deviation, minimum, and maximum will be calculated for continuous variables. The number of decimal places will be to plus two decimal places.
- Frequencies and percentages will be calculated for categorical data.
- Distribution of continuous variables and proportions of categorical variables will be tabulated by intervention group, and t-test and chi-square tests will be performed to evaluate if these variables are balanced across 4 intervention groups.
- Baseline is defined as the randomization visit.

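### The SAP's worst-case and best-case analyses give missing patients the same outcome in both arms, and no planned analysis lets that outcome differ by arm

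*SAP*

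**What the plan says.** - **Primary handling.** SAP 5.1 states "Missing endpoint data will not be imputed" and excludes patients with a missing endpoint from the primary analysis. Its expectation of loss is "Up to 3% of subjects have been estimated to drop out prior to end of follow-up before 90 days". It also says that missing data will be monitored across treatment groups during the study.
- **The promised check.** Protocol XVII.H, on losses to follow-up, excludes patients for whom nothing indicates the outcome and will then "carry out a worst case analysis to confirm the result of the primary analysis". The protocol does not define that analysis.
- **The only definition.** SAP 5.3.5 lists five scenarios. Two are per-protocol samples. Scenario (3) "includes those with the initial 90-day blood sample but are missing the confirmatory sample". Scenario (4) is run "assuming all those with missing endpoint data had events before 90 days (the worst case scenario". Scenario (5) is run "assuming all those with missing endpoint data had no events before 90 days (the best case scenario". Scenarios (3) to (5) make no distinction by arm.
- **Local-laboratory values.** Protocol XVII.F, on the adjustment for loss to follow-up, says "The study will permit secondary analysis of any SCr values assayed at a local laboratory", for specimens that could not be collected for the central laboratory. SAP 5.3.5 does not list this analysis.

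**The concern.** A complete-case comparison of two arms is at risk when missing patients in one arm fare differently from missing patients in the other. Giving every missing patient the same outcome does not probe that. If the numbers missing are similar, it adds about the same count to each arm (or none) and leaves the difference almost unchanged. The case least favourable to a claim of benefit is the opposed one: missing treated patients have events and missing controls do not. Neither document plans that case or any step towards it.

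What is at stake is how a positive result would be read. A report could say that the finding survived both worst-case and best-case analyses, when neither had varied the assumption that matters most. The creatinine component is the exposed part, because it needs a blood sample that record review and telephone contact cannot supply.

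**Working it through.** **Inputs.** 7,680 patients, equally allocated, so 3,840 v 3,840 at each margin (SAP 4). Event rates 8.70% control and 6.52% treated (Protocol XVII.F). Final level 0.024 (SAP 4). Loss 3% (SAP 5.1), applied here as missing endpoints in each arm: 0.03 × 3,840 = 115.2.

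**Reproducing the plan's sample size.** Per arm, n = [z(α/2)·√(2p̄(1−p̄)) + z(β)·√(p₁(1−p₁) + p₀(1−p₀))]² / (p₀−p₁)². With p₁=0.0652, p₀=0.0870, α=0.025 and 90% power the total is 7,342. With the protocol's final critical value of 2.25 it is 7,380. Dividing by 0.97 gives about 7,570 and 7,609, within 1.4% of the stated 7,680. The plan's own step, 7,450/0.97 = 7,680, also checks.

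**Test.** For treated events a of n₁ and control events c of n₀:

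log OR = ln[a(n₀−c) / (c(n₁−a))], SE = √(1/a + 1/(n₁−a) + 1/c + 1/(n₀−c)), z = log OR/SE.

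Observed events are 3,724.8 × 0.0652 = 242.9 treated and 3,724.8 × 0.0870 = 324.1 control, a gap of about 81. About 230 patients are missing in total.

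| Scenario, 3% missing per arm | Treated | Control | OR | z | p |
|---|---|---|---|---|---|
| Complete case | 242.9/3,725 | 324.1/3,725 | 0.73 | −3.54 | 0.0004 |
| SAP (4), all events | 358.1/3,840 | 439.3/3,840 | 0.80 | −3.03 | 0.0024 |
| SAP (5), all non-events | 242.9/3,840 | 324.1/3,840 | 0.73 | −3.53 | 0.0004 |
| Arm-opposed | 358.1/3,840 | 324.1/3,840 | 1.12 | +1.36 | 0.17 |

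The arm-opposed 95% interval is 0.95 to 1.31. Under (4) and (5) the risk difference moves only from 2.18 to 2.11 percentage points. Even at 10% missing per arm, scenario (4) still passes (p=0.022).

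**Tipping point.** Let missing controls have events at 8.7%, so that controls total 3,840 × 0.087 = 334.1. Significance at 0.024 is lost when treated events reach about 280.4 (OR 0.827, z about −2.25). The event rate needed among missing treated patients is then:

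- 3% missing: (280.4 − 242.9)/115.2 = about 33%
- 5% missing: (280.5 − 237.8)/192 = about 22%
- 10% missing: (280.6 − 225.3)/384 = about 14%

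The documents give only 3%. The higher rates are assumptions. The top of the range matches the 90% site follow-up threshold in Protocol XIV.E.

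**When scenario (4) does respond** (imbalances and the smaller effect are assumed):

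- 3.5% v 2.5% missing, treated v control, design effect: OR 0.88, p=0.087.
- 4% v 2% missing, design effect: OR 0.97, p=0.70.
- 3% missing per arm, 18% reduction (treated rate 0.82 × 8.7% = 7.13%): p moves from 0.012 to 0.031, above 0.024.

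**The case against.** A reader might infer that the two scenarios cannot test whether missing data could overturn a positive result. The documents do not support that. Scenario (4) loses significance under unequal missingness and for a borderline effect, as shown above. It also does so in a constructed false positive with no true effect, 5% missing per arm, 40% events among missing treated patients and 8.7% among missing controls (all assumed). There the complete case gives p=0.009 and scenario (5) repeats it, but scenario (4) gives p=0.038. Unequal dropout is also the visible warning sign, and SAP 5.1 monitors it. So (4) should stay.

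A reader might also infer that known deaths and dialysis starts are discarded when the creatinine is missing. That is not what the plan says. Under SAP 3.5.1 any one of the three events makes the patient an endpoint case, and the protocol excludes only patients with no information on outcome.

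The arm-opposed extreme is itself severe. At 1% missing per arm it already gives p=0.062 for the full design effect, so as a confirmation rule it would reject almost any real benefit of this size. Patients, providers and site staff are blinded (Protocol VII.C), which makes a large split in outcome between missing patients less likely. Both points stand. They argue for a graded tipping-point display in place of a single extreme.

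The local-laboratory analysis would recover some values, and scenario (3) deals with missing confirmatory samples. Neither examines what remains missing.

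**Conclusion.** The point holds in limited form. Scenarios (4) and (5) use one rule for both arms, so with similar missingness they hardly change the comparison, and no planned analysis lets outcomes among missing patients differ by arm. At the plan's own 3% loss, both show comfortable significance for a design-size effect, while the opposed assignment loses it and reverses the direction of the estimate. The informative figure is the tipping point of about 33% events among missing treated patients against 8.7% among missing controls. The current plan gives a reader no such figure to judge.

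This is a weakness in the sensitivity section. It does not show that the primary analysis is biased. The figures rest on expected counts at one margin, equal missingness unless stated, and the 7,680 patients without the additional 1,000 from non-VA sites.

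**What to change.** In SAP 5.3.5:

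1. Keep scenarios (4) and (5), relabelled as all missing counted as events and all missing counted as non-events.
2. Add, for each main effect, a tipping-point grid over arm-specific event rates among missing patients. Show the two arm-opposed extremes as the ends of the grid, and state that they are not a pass/fail confirmation rule.
3. List the analysis of in-window local-laboratory creatinine that Protocol XVII.F already permits.

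The cost is a paragraph of SAP text and a few more model runs, with no new data and no change to sample size or alpha. The extreme corner of the grid will look unfavourable even for a real effect, and the text should say so in advance.

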5.4. Secondary Analysis

For each of the five secondary endpoint events listed in **3.5.2** we will follow the same analytic strategy as the primary analysis described in **5.3**, where the odds of having an outcome will be estimated by modeling the outcome as a binary indicator of presence or absence of an event.

We will derive the Odds Ratios (i.e., the odds of the event of interest at 90 days post angioplasty among those allocated to IV isotonic sodium bicarbonate therapy compared to those allocated to IV isotonic saline, and among those allocated to NAC compared to those allocated to Placebo), and test for statistical significance of these odds ratios at $p=0.025$ level.

5.5. Tertiary Analysis

Data for this exploratory tertiary objective will be accrued from the US Renal Data System Warehouse, NDI database, SSDI database, and the VHA Corporate Data Warehouse (CDW).

For each of the 2 tertiary endpoint events listed in **3.5.3** we will follow the same analytic strategy as the primary and secondary analyses described in 5.4 above.

5.6. Interim Analysis

This study is expected to enroll 7680 subjects over a 2.5 years (or 30 month) recruitment period. At 18 months, i.e., after 15 months of recruitment plus 3 months of follow-up, approximately half or 3840 subjects are expected to be enrolled with primary endpoint events occurring in roughly 292 subjects (7.6%). Using the O'Brien-Fleming procedure, we will carry out an interim analysis to determine if either intervention shows a substantial beneficial effect.

We will compare the proportion of subjects with a MAKE-D event among those with and without the use of bicarbonate and among those with and without the use of NAC.

We will follow the same analytic strategy as described in **5.3** for primary analysis, where the odds of having an outcome will be estimated by modeling the outcome as a binary indicator of presence or absence of the MAKE-D event.

We will derive the Odds Ratios (i.e., the odds of the event of interest at 90 days post angioplasty among those allocated to IV isotonic sodium bicarbonate therapy compared to those allocated to IV isotonic saline, and among those allocated to NAC compared to those allocated to Placebo), and test for statistical significance of these odds ratios at $p=0.001$ level, assuming no interaction between the active interventions.

If the Wald Chi-square test has $p \leq 0.001$ for regression coefficient β_1 in Model 2, then the null hypothesis of $H_0: \beta_1 = 0$ will be rejected and alternative hypothesis of $H_a: \beta_1 \neq 0$ accepted. If the 95% Confidence Interval of the Odds Ratio does not include 1 and $\beta_1 < 0$, we can conclude that Bicarb is superior to Saline. Conversely, if the 95% Confidence Interval of the Odds Ratio does not include 1 and $\beta_1 > 0$, we can conclude that Bicarb is not superior to Saline.

Similarly, if the Wald Chi-square $p \leq 0.001$ for regression coefficient β_2 in Model 2, then the null hypothesis of $H_0: \beta_2 = 0$ will be rejected and alternative hypothesis $H_a: \beta_2 \neq 0$ accepted. If the 95% Confidence Interval of the Odds Ratio does not include 1 and $\beta_2 < 0$, we can conclude that NAC is superior to Placebo. Conversely, if 95% Confidence Interval of the

Odds Ratio does not include 1 and $\beta_2 > 0$, we can conclude that NAC is not superior to Saline.

5.6.1. Futility Analysis

If requested by the DMC, a futility analysis that includes conditional **power** estimation will be conducted to determine the probability of observing a significant result assuming the distribution of future event rates from additional data from the second half of the study follow 3 scenarios. These assumptions are:

no-change scenario – future event rates are same as currently observed,
expected scenario – future event rates are as proposed in the protocol, and
extreme scenario – all new events at the currently observed rate are in the control group.

6. Sample SAS Code

```
proc genmod;  
class outcome Bicarb NAC;  
model outcome = Bicarb NAC/ error=bin link=logit type3;  
make 'parmest' out=parmest;  
run;
```

```
/*to get estimated odds ratios*/  
data parmest;  
set parmest;  
if df gt 0;  
OR=exp(estimate);  
low_OR=exp(estimate-1.96*stderr);  
hi_OR=exp(estimate+1.96*stderr);  
run;
```

```
proc print data=parmest label noobs;  
title 'Estimated Odds Ratios and 95% CIs';  
var parm level1 estimate stderr or low_OR hi_OR;  
format estimate stderr OR low_OR hi_OR 6.3;  
label  
parm='Parameter'  
level1='Level'  
estimate='Beta estimate'  
stderr='Standard Error'  
OR='Estimated OR'  
low_OR='Lower limit 95% CI'
```

hi_OR='Upper limit 95% CI';
run;

7. Data Monitoring Committee Reports

Data and study progress will be monitored by the study executive committee and by the Data Monitoring Committee. The DMC will review the study progress and safety semiannually with additional meetings and communications as needed.

All reports will be generated in conjunction with the Data Management department using SQL and SAS.

Updated Shell tables can be found on Sharepoint using the following link

<https://vaww.ord.research.va.gov/CSP/Boston/csp578/centralfile/Data%20Monitoring%20Committee/Forms/AllItems.aspx?RootFolder=%2fCSP%2fBoston%2fcsp578%2fcentralfile%2fData%20Monitoring%20Committee%2f6%2e%20DMC%20Reports%20Shell%20Tables&FolderCTID=&View=%7b2F07C9DC%2d37B3%2d456C%2dAFDC%2d7F19514038EE%7d>

7.1. Analytic Sample for DMC Reports

All subjects randomized more than six weeks prior to the DMC meeting date will be included in the analytic cohort for the upcoming DMC report, and all data collected up to four weeks prior to the DMC meeting date will be analyzed. This allows for two weeks lag time for submission of data from sites.

7.2. Outline of DMC Reports

Shell tables with algorithm annotated for creating the table content are provided in section 8 below. The report is divided into four sections to cover subject disposition, baseline assessment, follow-up assessment, and safety assessment. Following is the list of tables to be included within each of these 4 sections. Revision to this list, if any, will be discussed at the first DMC meeting to be held within six months of the initiation of subject enrollment in the VA sites.

7.2.1. Section A: Subject Disposition

Figure A1. CONSORT Diagram for CSP578

Figure A2. Overall Study Enrollment

Figure A3. Enrollment by Site

Table A4. Protocol Deviations

Table A5. Terminations

Table A6. Form Completion, by Form Type

Table A7. Form Completion, by Site

7.2.2. Section B: Baseline Assessment

Table B1. Patient Characteristics

Table B2. Military Service, VA sites only

Table B3. Medical History and Baseline Assessments

Table B4. Baseline Labs

Table B5. Study Procedure - Part I

Table B6. Study Procedure – Part II

Table B7. Study Medication Capsule Administration

Table B8. Study IV Fluid Administration

Table B9. Non-Study Drugs Pre- and Post- Procedure

Table B10. Sample Specimens Collected

7.2.3. Section C: Follow-up Assessment

Table C1. Post Procedure Assessment , Part I

Table C2. Post Procedure Assessment, Part II

Table C3. Study Outcome Events

7.2.4. Section D: Safety Assessment

Table D1. Rates of Non-Serious Adverse Events (NAEs) and Serious Adverse Events (SAEs), by Site

Table D2. Summary of Non-Serious Adverse Events

Table D3. Summary of Serious Adverse Events

Table D4. Non-Serious Adverse Events by System Organ Class and Preferred Term

Table D5. Serious Adverse Events by System Organ Class and Preferred Term

8. References

